6.1.7.2 Treatment Period

Patients will be treated at 21 ± 3 day intervals. Patient must begin cycle 1 within 21 days of signing the IRB approved informed consent document and after the screening assessments have been performed and reports have been reviewed to confirm eligibility. Screening clinical evaluations and laboratory assessments may be used as the Cycle 1/ Day 1 evaluations if they are completed within 7 days prior to trial treatment administration.

Treatment will be administered by qualified and trained site personnel in a hospital, clinic, or other outpatient setting appropriate for chemotherapeutic infusions.

For subsequent cycles, all assessments must be conducted prior to treatment administration and within 72 hours (except those noted), or if medical or scheduling conditions require a delay.

Day 1 of each cycle

- Inclusion/exclusion review (Cycle 1 only)
- Directed physical exam
- Vital signs
- Measurement of weight (kg) and BSA calculation prior to dosing (After Cycle 1, the BSA only needs to be changed if there has been a change $> 10\%$ in body weight from Cycle 1 /Day 1)
- ECOG Performance Status (Appendix 4)
- Hematology: CBC with differential and platelet count. Results must be reviewed prior to treatment initiation to ensure patient still meets inclusion criteria.
- Serum chemistries (refer to Table 9). Results must be reviewed prior to treatment initiation to ensure patient still meets inclusion criteria.
- CA19-9 (C1/D1)

Every other cycle only: TSH, T3, Free T4, and PTH (not required at C1/Day 1 if completed within 21 days). Results must be reviewed prior to treatment initiation. To be repeated every other cycle, i.e. prior to cycle 3, 5, 7, 9, etc.

- Urinalysis
- Serum β -HCG pregnancy test. Results must be reviewed prior to treatment initiation confirming a negative serum β -HCG for women of child-bearing potential and documentation of the patients confirmation of preferred acceptable method of contraception per Section 4.7.2 starting from the day of trial treatment initiation (refer to Section 4.7.2 for more details).

- AEs using the NCI CTCAE V4.0 (Appendix 3)
- Concomitant medication notation of all medications taken within the 30 days prior to C1/D1
- Provide Fecal Swab collection kit and review instructions (Appendix 9) with patient for return of sample on Day 3
- Patient to complete the Patient Personalized Clinical Benefit (PPCB) App (Appendix 6)
- Paricalcitol administration
- Pembrolizumab administration

Day 3, 5, 8, 10, 12, 15, 17, and 19 (\pm 1 day) of each cycle

- Vital signs
- AEs using the NCI CTCAE (Appendix 3)
- Concomitant medication notation
- **Day 8 and 15 of each cycle only:** Directed physical exam, including weight
- **Day 8 and 15 of each cycle only:** ECOG Performance Status
- **Day 8 and 15 of each cycle only:** Hematology: CBC with differential and platelet count - results must be reviewed prior to paricalcitol administration
- **Day 8 and 15 of each cycle only:** Serum chemistries (refer to Table 9) - results must be reviewed prior to paricalcitol administration
- **Day 8 and 15 of each cycle only:** Patient to complete the Patient Personalized Clinical Benefit (PPCB) App (Appendix 6)
- **Day 19 Only:** Provide Fecal Swab collection kit and review instructions with patient for return of sample on Day 1 on next treatment cycle
- Paricalcitol administration

Week 9 (+/- 1 week)

- Optional repeat biopsy refer to Section 6.1.2.8
- Central Lab Blood Sample, 2 X 10 mL vials refer to Section 6.1.2.7

End of 3 treatment cycles (every 9 ± 1 weeks) until disease progression or end of trial, whichever comes first

- CT/MRI scan to evaluate disease status (using same imaging method as Baseline). Obtain De-identified dicomm encoded CT scan for central lab (Appendix 7).

Note: In order to more precisely determine time to progression, the investigator is encouraged to obtain radiological assessments and CA19-9 values earlier if there is a strong clinical suspicion of disease progression. In order to either confirm or refute the clinical impression.

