3.4 Primary Endpoints

The percent of patients with radiographic disease progression according to RECIST 1.1 at 6 months.

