4.9 Patient Replacement Strategy

Patients who are randomized to the trial but who then do not go on to initiate trial treatment, for any reason, will be replaced. The reason for not initiating treatment will be documented by the investigator. Patients who initiate trial treatment and discontinue from the trial for any reason will not be replaced. Patients who discontinue treatment without progression will be followed to determine their disease status every 90 days by phone until the trial ends.

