6.1.2.6 Tumor Imaging and Assessment of Disease

The patient's pancreatic cancer will be evaluated by the investigator based on tumor assessments using RECIST 1.1 and iRECIST criteria (Appendix 5).

Tumor assessments for evaluation of response will be conducted using CT or MRI, approximately every 9 ± 1 weeks until trial discontinuation or disease progression, whichever is later. All sites of disease must be followed using the same baseline assessment method.

CT is the preferred imaging modality for this study. I.V. contrast should be administered, unless medically contraindicated.

If CT with I.V. contrast is contraindicated, the alternative is to acquire a CT of the chest without contrast and MRI of the abdomen and pelvis with gadolinium contrast.

Other protocols, such as non-contrast CT of chest abdomen pelvis, should not be performed. For CT scans oral contrast should be administered in addition to IV contrast. Radiolucent agents (e.g., water) are generally preferred over radiopaque agents (e.g., iodine and barium-based agents).

All target lesions will be measured by consistent imaging techniques for each patient throughout the trial. Suitable imaging techniques include CT-scan, or MRI. The same technique should be used for each evaluation in an individual patient. Copies of the scans must be available for review.

In addition, a central radiologist, blinded to the treatment assignment, will perform an independent read of each scan, assessing tumor response using RECIST 1.1 and iRECIST criteria (Appendix 5).

In the event that PD by RECIST 1.1 or iUPD is determined, a repeat scan must be performed within 4 - 6 weeks to confirm PD. Trial treatment may be continued during this time (past the initial PD assessment) but only if patient is clinically stable as defined by:

- No worsening of performance status

- No clinically relevant increase in disease related symptoms
- No requirement for intensified management of disease related symptoms (analgesics, radiation, palliative care)

If the investigator assesses a patient to have PD (defined by RECIST 1.1), the central radiologist will review the scan to confirm the PD, prior to the discontinuation of trial treatment.

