8.2 Sample Size Considerations

The primary endpoint is the percentage of patients progressing at 6 months. Based on a contemporary control of no maintenance after best response to prior chemotherapy⁸, the control arm with pembrolizumab alone is expected to have only 8% of patients with no progression at 6 months. To be of clinical interest, at least 58% of patients must be progression-free at 6 months on the pembrolizumab plus paricalcitol arm. A sample size of 12 patients per arm will provide 90% statistical power to detect this difference assuming a one-sided alpha level of 0.05. A one-sided test was selected as we are only interested in the combination if it decreases the percentage of patients progressing at 6 months. This sample size estimate was obtained using binomial enumeration of all possible outcomes to compare two independent binomial proportions (Pearson's chi-squared test) using PASS 15.¹⁸ A statistical concern is that the Pearson chi-squared test does not guarantee the alpha level. We confirmed that we have adequate statistical power using the Miettinen & Nurminen¹⁹ exact likelihood score method (89% power) using Pass 15.

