8.3.4 Analysis of Primary Endpoint - Disease progression at 6 months

All patients that receive trial treatment will be included in the analysis to determine the percentage of patients progressing by RECIST 1.1 criteria at 6 months when maintained on a combination regimen of paricalcitol plus pembrolizumab versus pembrolizumab alone. The 6-month time-point will be defined as 6 months (180 days) from the initial treatment (cycle 1/day 1). Statistical analysis will compare the proportion progression free at 6 months using a one-sided test of binomial proportions (equivalent to a Pearson's chi-squared test). If the assumptions of the Pearson's chi-squared test are not met, we will analyze the data using Barnard's exact unconditional test of equality, as implemented in StatXact²⁰

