7 STATISTICAL METHODOLOGY

7.1 STATISTICAL PROCEDURES

Primary outcome: Progression-free survival

The proportion of patients in each arm who are progression-free at 6-months will be compared using a one-sided test of binomial proportions (equivalent to a Pearson's chi-squared test). If the assumptions of the Pearson's chi-squared test are not met, Barnard's exact unconditional test of equality will be used, as implemented in StatXact.

Patients unevaluable for progression at 6-months due to a non-progression related event will be excluded from analysis.

Statistical comparison of progression-free survival between the two treatment arms will be performed using a log-rank test, with estimation of the hazards ratio using a Cox proportional hazards model. A sensitivity analysis will include patients with an outcome of death due to another cause (other than progressive disease), which will be considered a competing event for progression. Analysis will be performed using the Fine and Gray (1999) approach.

Secondary outcome 1: Toxicity

All adverse events (AE) occurring on or after C1/D1 will be summarized by body systems and per grade according to NCI-CTCAE Version 4. Additionally, all serious adverse events (SAE) and events of clinical interest (ECI) will be listed separately and tabulated. ECIs for this trial include an overdose of pembrolizumab and an elevated AST or ALT lab value, as defined in section 6.2.3.2 of the protocol. All patients who receive any amount of trial treatment will be included in the analysis. The proportion of patients in each arm with toxicity will be compared using a chi-squared test or Barnard's exact unconditional test of equality as outlined above.

Secondary outcome 2: Overall survival

Overall survival will be calculated for each arm using a Kaplan-Meier estimate. Statistical comparison of overall survival between the two treatment arms will be performed using a log-rank test, with estimation of the hazards ratio using a Cox proportional hazards model. Patients with an outcome of death due to another cause (other than progressive disease) will be considered a competing event for death. Analysis will be performed using the Fine and Gray (1999) approach.

Exploratory outcome 1: RECIST 1.1 versus iRECIST

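### For patients who stop treatment without progression before day 180, the protocol contradicts itself on whether scans continue, so the radiographic primary endpoint may have no scan near day 180

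*Protocol*

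**What the plan says.** **Endpoint.** Protocol 3.4 defines it as "The percent of patients with radiographic disease progression according to RECIST 1.1 at 6 months". Section 8.3.4 fixes the time point at 180 days from cycle 1 day 1 and includes every patient who received trial treatment.

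**Passages that continue imaging.** Protocol 6.1.2.6 and Table 7 footnote j schedule CT or MRI about every 9 ± 1 weeks "until trial discontinuation or disease progression, whichever is later". Table 8 footnote d uses the same later-of wording. Section 6.1.7.2 schedules the 9-weekly scans "until disease progression or end of trial, whichever comes first".

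**Passages that do not.** Section 4.9 says: "Patients who discontinue treatment without progression will be followed to determine their disease status every 90 days by phone until the trial ends". Section 5.0 moves patients to telephone contact every 90 days after the 30-day visit. The tumor imaging row of Table 8 is marked at EOT only; the 30-day and 90-day columns are empty.

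**Passages that leave it open.** Section 4.8 requires disease-status follow-up every 90 days until progression, non-study cancer treatment, consent withdrawal, loss to follow-up or end of trial, and names no method. Section 6.1.7.3 requires a scan at the EOT visit, within 5 days of the last dose. Section 6.1.7.4 lists no later scan.

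**Analysis.** SAP 6 treats a patient with a missing value as unevaluable at that time point, without imputation. SAP 7.1 adds: "Patients unevaluable for progression at 6-months due to a non-progression related event will be excluded from analysis".

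**The concern.** RECIST 1.1 progression (Appendix 5) rests on lesion measurements, new lesions or unequivocal growth of non-target disease. A telephone call supplies none of these. Whether an early stopper contributes to the primary endpoint therefore depends on which section the site follows.

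Such losses need not be random. Stopping for toxicity happens after randomization and may differ by arm, because only one arm receives paricalcitol. Section 4.9 does not replace treated patients who stop, and Section 8.2 states no allowance for loss. With 12 per arm, each missing patient carries weight, and a scan that was not taken cannot be recovered at analysis.

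**Working it through.** **1. The passages applied to one patient.** Take a patient who stops for toxicity at week 10 without progression.

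- 6.1.2.6, Table 7 footnote j, Table 8 footnote d: imaging continues to the later event, so until progression.
- 6.1.7.2: progression has not occurred, so scans continue until progression or end of trial.
- 4.9, 5.0 and the Table 8 row: EOT scan, then telephone only.

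The first two agree in substance for this patient; the third contradicts both. An undefined term adds to the uncertainty. Section 4.8 lists reasons for stopping treatment as reasons for leaving the trial, so trial discontinuation can be read as end of treatment, and a site may treat the patient as finished with scheduled imaging.

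**2. Which scan bears on day 180.** Nine weeks is 63 days, and the window is ± 7 days.

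- Scan 1: day 63 (56 to 70)
- Scan 2: day 126 (119 to 133)
- Scan 3: day 189 (182 to 196)

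The third scan is the one nearest day 180. Its whole window falls after day 180, and neither document names the scan that decides 6-month status. Under the telephone rule the week-10 stopper's last image is near day 70.

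**3. The plan's power figure.** Section 8.2 states: "A sample size of 12 patients per arm will provide 90% statistical power to detect this difference", "assuming a one-sided alpha level of 0.05". The progression-free rates are 8% and 58% (1/12 and 7/12 in the synopsis). The test statistic is

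Z = (p2 − p1) / √[p̄(1 − p̄)(1/n1 + 1/n2)], rejecting if Z ≥ 1.645,

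where p̄ is the pooled proportion. Power is the sum of the binomial probabilities of all rejecting outcomes. At 12 per arm this gives 90.3% (8% vs 58%) or 90.1% (1/12 vs 7/12). The Miettinen-Nurminen version, Z√(23/24), gives 89.0% or 88.8%. Both stated figures, 90% and 89%, reproduce.

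**4. Power after assumed losses.** Rates are 1/12 vs 7/12. Barnard here means the Z ordering with its cut-off raised until the maximum type I error is at most 0.05.

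| Evaluable per arm | Pearson | Barnard |
|---|---|---|
| 12 | 90.1% | 85.1% |
| 11 | 86.9% | 81.6% |
| 10 | 82.4% | 81.7% |

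With random loss at the same rate in both arms (8% vs 58%, Pearson), average power is 87.7% at 5% loss, 86.2% at 10%, 84.4% at 15%, 82.3% at 20% and 79.9% at 25%.

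**5. How far one or two patients move the result.** Counts are progression-free patients, control vs combination; p-values are one-sided.

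- 1/12 vs 4/12: Z = 0.2500/√[(5/24)(19/24)(1/12 + 1/12)] = 1.508. Pearson p = 0.066, Barnard p = 0.081.
- If two combination patients whose progression was never imaged are excluded, this becomes 1/12 vs 4/10: Z = 0.3167/√[(5/22)(17/22)(1/12 + 1/10)] = 1.765. Pearson p = 0.039, Barnard p = 0.0499.
- 1/12 vs 5/12: Z = 0.3333/√[(6/24)(18/24)(1/12 + 1/12)] = 1.886. Pearson p = 0.030.
- If one of those five lacks the scan and is excluded, this becomes 1/12 vs 4/11: Z = 0.2803/√[(5/23)(18/23)(1/12 + 1/11)] = 1.628. Pearson p = 0.052.

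**The case against.** **Most of the protocol favors continued imaging.** Besides the passages above, Appendix 5 asks sites to try to document objective progression after treatment stops, and puts assessments on a calendar unaffected by treatment delays. Section 6.1.7.4 starts survival follow-up only at confirmed progression or new therapy. On this view 4.9, 5.0 and the Table 8 row are outliers in a reconciliation error. That is fair, and it makes the repair easy. But Appendix 5 schedules no scan, and the outliers are where a site would look for off-treatment follow-up.

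**Later-of against first-of.** A reader might infer that 6.1.2.6 and 6.1.7.2 are themselves the conflict. The documents do not support that for these patients. The two sections compare different pairs of events, and read literally both continue scans in a stopper who has not progressed. The gap comes from the telephone rule and the Table 8 row.

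**No scan at all.** A reader might also infer this. It is too strong: the EOT scan is required, and a patient who has progressed at that scan is determined.

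**The SAP does not discard everything.** SAP 7.1 adds a log-rank and Cox comparison of progression-free survival, which can use follow-up before day 180. That stands, but the 6-month proportion is the primary endpoint, and there the exclusion applies.

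**The sizes are hypothetical.** This stands too. At 1/12 vs 4/12 the expected progression-free count is 5 × 12/24 = 2.5 per arm, so by the usual rule Barnard's test would apply, and 0.0499 is a bare crossing that needs two losses in one arm.

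**Conclusion.** The contradiction is real and reaches the primary endpoint. Under the telephone rule, a patient who stops without progression before day 180 has no scheduled scan after EOT, so usually none at or near day 180. The SAP then excludes that patient while Protocol 8.3.4 counts them.

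The size depends on assumed losses, because neither document gives a dropout rate. One loss per arm costs about 3 points of power with either test (90.1% to 86.9% for Pearson, 85.1% to 81.6% for Barnard). Two per arm leave about 82% with either. The shift in the result matters more than the power: with 12 per arm, one or two exclusions can carry it across 0.05 in either direction.

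A reader might infer that the exclusions will favor the combination. The documents give no basis for that pattern; the illustrations show sensitivity only. The point deserves correction because the missing data are avoidable and 6.1.2.6 already requires the scans.

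**What to change.** 1. Reconcile Protocol 4.8, 4.9, 5.0, 6.1.2.6, 6.1.7.2, Table 7 footnote j, and the Table 8 imaging row and footnote d into one imaging rule. Patients off treatment without progression keep the 9 ± 1 week calendar scans until RECIST 1.1 progression, or at least through the scan that determines day-180 status.
2. Name that scan. On the present grid it is the third, about day 189 (window 182 to 196).
3. Section 4.8 and Table 8 footnote a end disease-status follow-up at non-study cancer treatment, consent withdrawal or loss to follow-up. Keep these stops, or change them explicitly, so that the new rule does not override them silently.
4. Define trial discontinuation separately from end of treatment, and use telephone contact for survival only.
5. Align Protocol 8.3.4 with SAP 6 and 7.1 on how a treated patient without the deciding scan is counted.

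The cost is wording, plus one to three scans for each of the few early stoppers: three for a patient who stops before the first scan, one for a patient who stops after the second.

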6.1.7.3 End of Treatment (EOT)

The patient will continue on maintenance therapy until there is evidence of clear-cut tumor progression, has treatment ending toxicities, or withdraws from treatment (refer to section 4.8). The following assessments will be performed within 5 days after completing the last dose of trial medication or before the initiation of a new anti-cancer treatment, whichever comes first:

- Directed physical exam
- ECOG Performance Status (see Appendix 4)
- Vital signs
- ECG
- Hematology: CBC with differential and platelet count
- Serum chemistries
- TSH, T3, T4
- CA19-9 (or CEA or CA-125 if not expressers of CA19-9)
- Urinalysis
- Serum β -HCG pregnancy test (for WOCBP)
- Central lab blood sample, 2 X10 mL vials
- Concomitant medication
- Patient to complete the PPCB App (Appendix 6)

- Provide Fecal Swab collection kit and review instructions (Appendix 9) with patient for return of sample within 72 hours of collection (coordinate with 30 day Safety Follow-Up visit)
- CT/MRI scan to evaluate disease status (using same imaging method as Baseline). Obtain De-identified dicomm encoded CT scan for central lab (Appendix 7).
- AEs using the NCI CTCAE Version 4.0 (see Appendix 3)
- Review contraception use as required by protocol Section 4.7.2 (where applicable)
- Confirm contact information for patient and a designated family member and remind patient of FU telephone contact that will be conducted every 90 days for survival status following the 30 - day follow-up visit.

